4.0. Statistical Considerations

A: Sample Size calculation: Given that previous studies have attributed at least 50% improvement in the ability to tolerate milk(24) with an α of 0.05 and a power (1- β) of 0.80, a sample of 42 cases and 42 controls will be recruited.

B: Statistical Analysis: Statistical analyses will be performed using paired t-tests. A p value of <0.05 will be considered significant. Descriptive statistics of the variables including means, standard deviations and frequencies were computed for all study variables. The concentrations of milk –specific IgE, IgG and IgA, the size of the skin tests , T reg and Breg expression at the different study time-points will be compared with their baseline values using the one-sample paired t-test and to the control using a 2 sample t-test .

Multiple regression models will be used to assess factors associated with response to desensitization, including baseline demographic characteristics; gender; age; baseline SPT and specific IgE, Treg and Breg numbers, and vitamin D level.

5. Ethical Considerations

In the consent form given at study enrolment, participants will be advised that they will be randomly assigned to either oral immunotherapy or observation for a one year period. Participants will also be advised that their data will be shared only among the OIT study team. Participants in the observation control group who will not receive OIT treatment, will be told that they may to undergo such therapy after a year of observation and a positive oral food challenge.

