serological criteria, will be recruited for this study. 42 will undergo oral immunotherapy, while 42 will be followed as natural history controls but will be offered similar therapy, should it be successful, at the completion of one year. OIT subjects will initiate therapy with a 2-day rush desensitization treatment using oral doses of milk, in our Clinical Investigation Unit. They will then continue the highest tolerated dose of milk at home for two weeks. Subsequently, they will return for weekly increases in doses until a maximum of 200 ml of milk is ingested daily. The primary clinical outcome will be a comparison of the amount of milk consumed safely on oral challenge performed prior to OIT, when the OIT dose has reached its maximum (200 ml or highest tolerated dose) and after one year of therapy. Patients will also be followed with clinical symptom scores and adverse event diaries and we will monitor immunological parameters such as changes in milk-specific IgE, blocking antibodies (IgG4 and IgA) and regulatory T and B cells. We expect that we will be able to see important improvement in the ability to safely ingest milk and other dairy products, and this will be accompanied by significant decreases in IgE and increases in Regulatory T and B cells.

BACKGROUND INFORMATION:

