15 The impact of CMA: IgE mediated milk allergy is associated with a high frequency of unwanted reactions (12). In US surveys, it was ranked as second or third most common food requiring adrenalin treatment in children with food allergy (13, 14). This was due to the high frequency of dairy ingredients in common foods as well as medication and supplements (15, 16). Complete avoidance of dairy is thus difficult for families, and for the affected children and young adults.

The natural history of IgE mediated milk allergy is variable. It was reported that symptoms of CMA resolve for approximately 80% - 90% of children before the age of 5 (17). However, more recent studies indicate a later resolution of milk allergy and fewer children outgrowing CMA . In a study by Skripak et al, the median age for tolerance to cow's milk was 7 years \pm 11 months and at least 15% - 20% of their population retained their sensitivity into the second decade of life (18). This represents resolution at **older ages** than earlier studies (5). In addition, at least 20% of children who are diagnosed with CMA will have **life-long allergy** (5). The consequences of later resolution and prolonged allergy include important nutritional deficiency especially at critical times of bone growth and mineralization (19-21), in addition to the high risk of life-threatening events that accompany the increased exposures experienced by teens and young adults.

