To date several studies have examined oral immunotherapy (OIT) for milk, eggs, and peanut allergies. Several uncontrolled studies have been published, although few controlled trials of oral immunotherapy to milk have been performed. A recent meta-analysis found only 4 studies of oral immunotherapy for CMA that included control groups (24). The authors found that the protocols were overall successful, with up to 10 fold improvements in milk tolerance in treated patients compared to untreated or placebo treated controls. These protocols reveal encouraging results with significantly increased thresholds to ingesting milk after oral immunotherapy (25-28). However, all studies had relatively small sample sizes. The authors of the meta-analysis also observed that for each study, treatment was accompanied by a significant number of reactions to milk (24). Most reactions were mild to moderate, and none were life-threatening. The authors concluded that more controlled studies should be performed to determine the safest and most efficacious protocols, whereby patients have the maximum benefit with risks minimized.

1.7 Questions regarding OIT treatment for CMA: There are no known guidelines describing the optimal patient candidates for desensitization nor are there criteria for the safest and most effective dosing schedules. To date, published milk desensitization protocols start treatment with very small doses, and the doses are increased weekly or bi-weekly. Alternatively, “rush” protocols which perform the initial increases rapidly in hospital over a 1-3 day period are employed, in order to speed up treatment. Rush protocols appear to be effective, although may be associated with more side effects during the in-hospital period. Conclusions as to the optimal protocols are limited by the low number of studies performed with each one. Therefore, major questions exist regarding the efficacy of the immunotherapy, the quantity/ frequency of allergen consumption required to cause desensitization and the optimal protocol that can balance efficacy and minimize side effects.

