Withdrawal from therapy: Subjects will be carefully monitored during the in hospital rush therapy phase, as well as during the home OIT phase. Instructions for treatment of reactions will be provided as above. Patients who are enrolled will be informed that in previously published studies, minor allergic reactions are common in these protocols (mild itching, abdominal discomfort) but resolve with increased time on therapy. Subjects will be withdrawn if they cannot tolerate the low dose, rush desensitization phase, if they have more than 2 or more moderate or severe reactions during the home (maintenance) OIT phase, if they experience a rare or unforeseen complication such as severe flares of eczema or chronic gastrointestinal symptoms (e.g. development of eosinophilic esophagitis) and if the parents or subjects wish to voluntarily terminate therapy.

3.3.6 : Variables measured. The following variables will be measured in each patient:

A. The primary outcome measure will be the presence of desensitization defined by the ability to tolerate 200 ml of milk 1 year after the start of the trial. This is a qualitative variable with three categories: total desensitization (200 mL of cow's milk); partial desensitization (20–200 mL); and failed desensitization (<20 mL milk). Only patients presenting total desensitization were regarded as being successfully desensitized.

B. Secondary outcome measures will be:

1. Number and severity of adverse reactions occurring after oral exposure to milk during the desensitization and follow-up phases.
2. Minimum dose of milk that triggered symptoms during the desensitization protocols or challenge tests.
3. Days until desensitization was achieved.
4. Indices of desensitization :
 - a. Change in skin prick test weal size, comparing tape transferred, cpoputor measured diameters and areas of the skin tests to milk extract.
 - b. Levels of sIgE, sIgA and sIgG4 before desensitization, during follow-up and at the end of the study.
 - c. T and B reg before desensitization, during follow-up and at the end of the study.

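### Section 4.0 names no between-arm test for the yes/no primary endpoint, and its 42 per arm with 80% power cannot be verified from the inputs given

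*Combined protocol and SAP*

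**What the plan says.** Section 3.3.6 A sets the primary outcome as desensitisation, "defined by the ability to tolerate 200 ml of milk 1 year after the start of the trial". It lists three categories, but only total desensitisation counts as success, so the endpoint is in effect yes/no. The Experimental Approach summary gives a different one: "The primary clinical outcome will be a comparison of the amount of milk consumed safely on oral challenge", before OIT, at maximum dose and after one year.

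Section 4.0 A rests the sample size on the statement that "previous studies have attributed at least 50% improvement in the ability to tolerate milk(24"). With alpha 0.05 and power 0.80, it concludes that "a sample of 42 cases and 42 controls will be recruited". Section 1.6 describes the same source as showing "up to 10 fold improvements in milk tolerance in treated patients compared to untreated or placebo treated controls".

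Section 4.0 B opens with "Statistical analyses will be performed using paired t-tests". It then names a two-sample t-test against control for antibodies, skin-test size, Treg and Breg. Its regression models look for predictors of response, and the list of predictors does not include treatment arm.

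**The concern.** There are two linked gaps.

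The first is the test. A paired t-test compares each child with that child's own baseline. It does not compare OIT with control, and it does not suit a success/failure outcome. Children must fail a milk challenge to enter, so a within-child test on the OIT arm would count spontaneous resolution as benefit. The randomised control group is there to remove exactly that.

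The second is the sample size. With no scale for the 50%, no control or treated rate and no SD, the stated inputs do not determine an N. A reader cannot tell whether the randomised comparison is comfortably powered or weak.

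**Working it through.** **Inputs from the documents.** 42 per arm, alpha 0.05, power 0.80 and 50% improvement (4.0 A); yes/no endpoint at 1 year (3.3.6 A). Not given: sidedness, scale of the 50%, arm rates, SD, dropout. I assume a two-sided test. Every arm rate below is an assumption.

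**Can 42 be reproduced?** Not from the stated inputs alone. For two proportions,

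n per arm = [1.960·√(2p̄(1−p̄)) + 0.842·√(pC(1−pC) + pT(1−pT))]² / (pT − pC)²

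where p̄ is the mean of the control rate pC and the treated rate pT. Both rates have to be supplied. Power at 42 per arm is by exact enumeration over both binomial counts.

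**Reading 1: +50 percentage points.** The largest n is at 25 versus 75%: (1.960 × 0.7071 + 0.842 × 0.6124)² / 0.25 = 3.615 / 0.25 = 14.5, so 15 per arm. At 0 versus 50% it is 11. Over control rates from 0 to 50%, the lowest power at 42 per arm is 99.9% (chi-square) or 99.7% (Fisher).

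**Reading 2: 1.5-fold success rate.**

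| Control vs OIT | n per arm for 80% | Power at 42, chi-square | Power at 42, Fisher |
|---|---|---|---|
| 10 vs 15% | 686 | 11% | 6% |
| 21 vs 31.5% | 275 | 20% | 14% |
| 33 vs 49.5% | 139 | 36% | 28% |
| 44 vs 66% | 80 | 57% | 48% |
| 55.5 vs 83.3% | about 42 | 81% | 74% |

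**Reading 3: failures halved.** From 60% to 30%, that is success 40 versus 70%: (1.960 × 0.7036 + 0.842 × 0.6708)² / 0.09 = 3.777 / 0.09 = 42.0. Power at 42 is 83% (chi-square) or 76% (Fisher).

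**Reading 4: OIT success of 50% against 21% in controls.** n = 41.5, so 42. Power at 42 is 82% (chi-square) or 75% (Fisher).

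**Reading 5: amount of milk, two-sample comparison.** The detectable standardised difference at 42 per arm is (1.960 + 0.842) × √(2/42) = 0.611. A 50% difference in means then needs an SD of 0.5 / 0.611 = 0.82 of the control mean. No SD is given.

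Readings 3 to 5 reach about 42, each with a value that the documents do not state.

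**Is the endpoint observed in both arms?** Section 3.2 has subjects challenged before desensitisation and after treatment. The Control Subjects paragraph lists skin tests, blood tests and diaries, with no challenge. Section 5 mentions a positive challenge after a year of observation as the gateway to later OIT. These passages do not clearly give controls a 1-year result for the primary endpoint.

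**The case against.** The strongest reply is that missing inputs are not an error. No arm rates are stated for any reading, and halving failures is as much a 50% improvement as a 1.5-fold success rate. That stands: the arithmetic does not show the 80% to be wrong.

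The 1.5-fold reading is also arguably the least natural. Every child reacted at entry, so control success may be low. At 10 versus 15% the difference would be 4.2 against 6.3 children per arm, which fits poorly with a source described as showing up to 10-fold gains. That stands too.

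A reader might infer a ceiling of 57% power for the 1.5-fold reading from the natural-history figures in the section on the impact of CMA. One is a persistence figure: "at least 15% - 20% of their population retained their sensitivity into the second decade of life". The other is the age of resolution, where the section reports that "the median age for tolerance to cow's milk was 7 years", with a margin of 11 months either side. With half still allergic at the median and 15% at age 10, constant yearly resolution is 1 − (0.15/0.50)^(1/3) = 33%. Starting from 7 years 11 months (2.083 years to age 10), it is 44%. The documents do not support this as a ceiling:

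- Constant resolution is assumed. The same two points allow 1 − 0.15/0.50 = 70% in a single year.
- The ± 11 months is undefined and is being used as a range.
- The median may describe only children who became tolerant. Then 1 − 0.85/2 = 57.5% remain allergic at that age, the rate becomes 1 − (0.15/0.575)^(1/2.083) = 47.5%, and power is about 64%.

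On the test, it can be said that paired t-tests fit the before-and-after outcome in the Experimental Approach summary, and that a between-arm comparison is implied by randomising. But the summary outcome is not the one in 3.3.6 A, and the two-sample test in 4.0 B is tied to a list that omits the primary endpoint.

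**Conclusion.** The point holds in two parts.

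1. As written, 4.0 B provides no valid between-arm comparison of the primary endpoint. This follows from the text and needs no numerical assumption.
2. The 42 per arm with 80% power is unverifiable. It would be above 99% for +50 points, in which case 80% is not the design's power. It would be about 11% to 57% for a 1.5-fold rate at assumed control rates of 10% to 44%, and about 80% under several other readings.

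A reader might conclude that the trial is underpowered, or that the 80% must be wrong one way or the other. The documents support neither. The power figures assume a two-sided 5% test, all 84 children analysed, and arm rates that I supplied.

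**What to change.** In 4.0 B, make the primary analysis a two-sided 5% between-arm test of total desensitisation (yes/no) at 1 year, OIT versus control, with all randomised children in their assigned arm. Fisher's exact test would do, as would a test stratified by sex to match the randomisation. Keep paired t-tests for within-arm changes only.

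State that both arms have the 1-year milk challenge on which the endpoint depends, and reconcile section 3.2, the Control Subjects paragraph and section 5 accordingly.

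In 4.0 A, say which meaning of 50% was used, give both arm rates (or the SD, if the amount of milk was the basis) with their source, and restate the power of 42 per arm for the named test.

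The cost is a rewritten sentence in 4.0 A, a line in 4.0 B and a clarification of control-arm assessments. If controls were not already due a 1-year challenge, that visit is the one real addition. Nothing here calls for a larger N.

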Through a process of stratified randomization (according to sex), participants will be randomly assigned to one of 2 study groups. The first group will receive active desensitization, and the second group will not receive any treatment but will be followed up regularly (Appendix A Table 2). Desensitization will be offered to the observation groups following the trial, should the outcome be successful in the treatment group.

3.2 Oral challenge test to milk. Prior to initiating desensitization and following treatment, the subjects will undergo a placebo controlled oral challenge to milk. These challenges will determine the level at which the children react and will be the baseline to follow their improvement in oral tolerance following therapy.

Oral challenges will be single blinded and will be performed with fresh cow's milk, with increasing doses taken orally every 10 to 15 minutes up to a total of 150ml of milk (doses of 0.1, 0.3, 1.0, 3.0, 10.0, 30.0, 45ml, 60 mL) ^{(49,82) (83)}. Patients will receive 2 challenges per day, 1 placebo and 1 with the active substance (milk). Nurses in the Medical Day Unit/Center for Investigative Medicine will prepare the food and randomize the placebo challenges. Unless contraindicated, the placebo will be soy or rice-based milk. If the challenge is negative after 150 ml of milk, results will be confirmed by means of open challenge, using 250ml of yogurt or ice cream 1 hour after completion of the blinded portion(29) according to the recommendations of the European Academy of Allergology and Clinical Immunology (5). After completing the challenge, patients will be kept under observation for at least 2 hours. Only objective symptoms will be considered to be indicative of a positive allergic reaction (29). Food challenges will be scored as positive if a single symptom or any of the following objective clinical reactions will be observed: urticaria, angioedema, wheezing, rhinitis, vomiting, diarrhea, protracted abdominal pain, exacerbation of atopic dermatitis, or shock. A single episode of vomiting will not be considered as a positive reaction, while severe and repetitive vomiting will. If the challenge is **negative**, ie, the subject is asymptomatic, he/she will be excluded from the study. Based on our experience, approximately 80% of those subjects ages 6 or greater, with positive history and positive skin tests, approached will fail the oral challenge and thus be eligible.

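### As written, Section 4.0.B gives no OIT-versus-control test for the three-category primary outcome; its general method is a within-patient t-test

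*Combined protocol and SAP*

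**What the plan says.** Section 3.3.6.A defines the primary outcome as desensitization one year after the start of the trial. "This is a qualitative variable with three categories": total (200 ml of milk), partial (20–200 ml) and failed (under 20 ml). It adds: "Only patients presenting total desensitization were regarded as being successfully desensitized".

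The allocation paragraph at the end of Section 3.1 sets up the comparison: "Through a process of stratified randomization (according to sex), participants will be randomly assigned to one of 2 study groups". One group receives OIT and the other is observed.

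Section 4.0.B contains these analysis statements:

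- A general one: "Statistical analyses will be performed using paired t-tests".
- For milk-specific antibodies, skin test size, Treg and Breg only, values "will be compared with their baseline values using the one-sample paired t-test and to the control using a 2 sample t-test".
- A model of response: "Multiple regression models will be used to assess factors associated with response to desensitization, including baseline demographic characteristics". The listed factors are baseline characteristics; study arm is not among them.
- Descriptive means, standard deviations and frequencies.

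The Experimental Approach summary gives a different primary outcome: "The primary clinical outcome will be a comparison of the amount of milk consumed safely on oral challenge performed prior to OIT". It sets that starting volume against two later challenges, one at the top OIT dose and one at a year.

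**The concern.** Objective 1 is the efficacy of OIT, and the randomised control arm is there to answer it. The general method in 4.0.B compares each patient with himself or herself. It would suit the before-and-after milk volume in the summary, but not a one-year category, and it makes no use of controls.

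Two things are at stake. First, the between-arm test, effect estimate, analysis population and missing-data rule for the main question could all be chosen after the data are seen. Second, a before-and-after analysis would credit to OIT any tolerance that develops without treatment. The Control Subjects paragraph (the second of the sections numbered 3.3.4) foresees exactly that, since it offers OIT at the end only to controls who have not become tolerant on their own. Section 3.2 excludes anyone who passes the baseline challenge, so from that starting point the outcome can only stay the same or improve.

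**Working it through.** **1. Is there a between-arm test for the primary outcome?** I took the statements of 4.0.B in turn.

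| Statement in 4.0.B | Uses controls? | Applies to the 3.3.6.A outcome? |
|---|---|---|
| Paired t-test, general | No | Not suited to a three-category result |
| Two-sample t-test | Yes | No; laboratory and skin measures only |
| Multiple regression | Arm not listed | Models response, not the arm effect |
| Frequencies | Descriptive | No test |

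No other section names one.

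**2. The plan's own figure.** Section 4.0.A gives 42 per arm from alpha 0.05, power 0.80 and an improvement of at least 50%. It states no control rate, SD, test or sidedness, so 42 cannot be reproduced from those inputs and does not reveal the intended test. Using n = [z(α/2)·√(2p̄q̄) + z(β)·√(p1q1 + p2q2)]² / (p1 − p2)², two-sided and uncorrected:

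- A 50-point absolute difference needs 11 to 15 per arm.
- A 50% relative increase needs from 294 (20% v 30%) down to 22 (65% v 97.5%).
- 30% v 60% gives (1.960 × 0.7036 + 0.842 × 0.6708)² / 0.09 = 42.0, but neither rate is in the documents.

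**3. What a within-arm test would do.** Code success as 0 for all at baseline. With k successes among n = 42 OIT patients, the paired statistic is t = √[k(n − 1)/(n − k)] on 41 df.

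- k = 3: √(3 × 41/39) = 1.776, p = 0.083.
- k = 4: √(4 × 41/38) = 2.077, p = 0.044.

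Four successes are enough, whatever happens in controls. If OIT had no effect and the one-year spontaneous success rate were 5%, 10% or 20% (assumed), the chance of at least 4 of 42 is 15.7%, 61.6% or 97.9%. A two-sided Fisher test between arms would reject 0.5%, 1.8% or 2.9% of the time.

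**4. What the control arm adds.** Take 21/42 OIT successes (assumed). A before-and-after reading is 50% in every case. Newcombe 95% intervals for the risk difference are:

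| Control successes of 42 | Difference, points | 95% CI |
|---|---|---|
| 0 | 50 | 33 to 64 |
| 4 | 40 | 21 to 56 |
| 8 | 31 | 11 to 48 |

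**5. Is a between-arm test workable at 42 per arm?** Exact Fisher power, two-sided 0.05, all rates assumed:

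| OIT success | Control 10% | 15% | 20% |
|---|---|---|---|
| 40% | 87% | 67% | 44% |
| 50% | 98% | 92% | 78% |
| 60% | >99% | 99% | 96% |

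A sex-stratified Cochran-Mantel-Haenszel test at 50% v 20% has simulated power of 84% without continuity correction and 78% with it, so the plan must say which is used.

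**6. Is the outcome measured in both arms at one year?**

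- The summary places a challenge after one year of therapy; 1.13 at the end of OIT and one month after stopping; 3.2 before and after treatment.
- Section 3.3.3 gives patients who reach 200 ml a challenge after one month at that dose, with a 300 ml maximum. It states a 12-month challenge only for those below 200 ml.
- Appendix C lists a post-treatment challenge only at Visit 24, one month after cessation.
- For controls, the Control Subjects paragraph lists skin tests, blood tests and diaries. Section 5 mentions a positive challenge after a year only in connection with being offered OIT.
- On volume, the doses in 3.2 sum to 0.1 + 0.3 + 1 + 3 + 10 + 30 + 45 + 60 = 149.4 ml, against a 200 ml success criterion and the 300 ml maximum in 3.3.3.

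This bears on missing data. Suppose true success is 50% v 20% and half the controls, at random, have no challenge (all assumed). Counting those controls as failures gives 20% × 0.5 = 10%, so the difference reads 40 points instead of 30. In the other direction, OIT patients who passed 300 ml but have no one-year challenge would be scored as failures.

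**The case against.** The strongest reply is that 4.0.B never assigns the paired t-test to the primary outcome: it makes one loose general statement and then turns to laboratory measures. Other text points to a comparison of arms. Section 4.0.A sizes the trial as two groups on the ability to tolerate milk, the allocation paragraph makes later OIT for controls depend on success in the treated group, and the regression list opens with a word that leaves it non-exhaustive.

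This stands as far as it goes. A reader might infer that the sponsor means to analyse efficacy by paired t-test alone, or to disregard the controls. The documents do not support either: they show between-arm intent, and controls are used for the laboratory and skin measures. But intent names no test, estimate or population, and an unlisted regression term is not pre-specified.

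Two other defences fail. A paired test could be computed on the summary's milk volume, but the times listed there are all relative to OIT, so it is still not a randomised comparison. The cross-over label in the summary does not help either, since only controls may switch, after a year, and no between-period analysis is described.

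**Conclusion.** The point holds and must be fixed. The gap rests on the text alone, not on any assumed rate: the plan as written has no OIT-versus-control test for its primary outcome, and the general method it does state is unsuited to that outcome.

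The size of the resulting bias cannot be given, because the documents state no one-year spontaneous resolution rate for this age group. The rejection probabilities in step 3 are illustrations and should not be read as the trial's error rate. Nor do the power figures show that 42 per arm is enough. They show that a between-arm test is feasible over part of the range; at 40% v 20%, for example, Fisher power is only 44%.

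**What to change.** **Precondition.** Reconcile the summary, 1.13, 3.2, 3.3.3, Control Subjects, 3.3.6.A, Section 5 and Appendix C on whether and when both arms have the one-year challenge, and on how the challenge volumes relate to the 200 ml criterion. The between-arm test cannot be run fairly until this is done.

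**Then, in 4.0.B, for the primary outcome only,** replace the general paired t-test statement with:

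- one two-sided comparison of the proportion totally desensitized at one year, OIT versus control;
- all randomised participants, in their assigned arm;
- a test that accounts for the sex stratum, for example Cochran-Mantel-Haenszel, stating whether a continuity correction is used;
- the risk difference with 95% CI.

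Make the summary's primary outcome match 3.3.6.A. Keep the t-tests for laboratory and skin measures.

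**Missing data.** Do not count missing results as failures until ascertainment is the same in both arms. Once it is, state the rule, with a sensitivity analysis that varies the assumption by arm.

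**Cost.** The changes to 4.0.B and the summary are wording, and randomisation is unaffected. The reconciliation may require a scheduled one-year challenge that some participants do not now clearly have. Once expected rates are stated, the 42 per arm should be checked against the chosen test.
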